- 9-Hole Peg Test (9HPT) is appointed gold standard for arm function.
- Criterion validity of strain and clinical performance tests will be performed as follows:
 - Normality and assumptions will be examined by means of scatterplots and linear regressions for strain and clinical performance test using gold standards as the dependant variables.

- Correlations between gold standards and strain will be assessed using Pearson's product-moment correlation coefficient r and/or Spearman's rank-order correlation coefficient ρ (rho).
- Correlations between gold standards and clinical performance tests will be assessed using Pearson's product-moment correlation coefficient r and/or Spearman's rank-order correlation coefficient ρ (rho).

Comparisons of criterion validity – baseline data

- For comparisons of criterion validity, we will use the results of the Spearman's rank-order correlation coefficient ρ (rho). This to ensure that the parameters are the same for all comparisons.
- Bootstrapping will be performed because independence cannot be expected, between correlation estimates from the same patient.
- Difference between criterion validity will be assessed using squared correlations on Fischer's Z-scale in combination with bootstrapping to define accelerated Bootstrap Confidence Intervals (95% BCa CI).

Study 2

Objective: To test the hypothesis that quality of gait using Gait Profile Score (GPS) based on nine different Gait Deviation Scores (GVS), as well as gait function using performance-based tests, spatiotemporal parameters, and self-perceived gait function, will improve in MS patients following two weeks of treatment with Fampridine. In addition, we hypothesize that changes in GPS are positively associated with changes in performance-based measures.

Participants

- A subgroup of participants, randomly allocated 3-dimensional gait analysis (3DGA).
- Age-matched reference group consisting of healthy people, collected in our own lab.

Outcome measures

- Demographic measures – at baseline
 - Age
 - Gender
 - Height and weight (from which Body Mass Index (BMI) was calculated)
 - Disease duration
 - EDSS [1]
 - Walking aids
- Gait Quality according to Baker et al 2009 [9] – baseline and change between baseline and 14-days follow-up
 - Gait Profile Score (GPS)
 - Gait Variable Scores (GVS)
 - Pelvic tilt
 - Pelvic obliquity

- Pelvic rotation
 - Hip flexion-extension
 - Hip abduction-adduction
 - Hip rotation
 - Knee flexion-extension

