- Demographic measures – at baseline
 - Age
 - Gender
 - Expanded Disability Status Score (EDSS) [1]
 - Multiple Sclerosis Impairment Scale (MSIS) [2]
 - Disease duration
 - Sub-diagnosis (MS)
 - Medical treatment (MS)
 - Walking aids
 - Smoking status
 - Alcohol intake

- Biomarkers – change/baseline
 - Plasma IFN-gamma (pg/mL)
 - Plasma IL-2 (pg/mL)
 - Plasma IL-4 (pg/mL)
 - Plasma IL-8 (pg/mL)
 - Plasma IL-17 (pg/ml)
 - Plasma TNF (pg/mL)
 - Plasma TNF-RI (pg/mL)
 - Plasma TNF-RII (pg/mL)
 - Neurofilament light chain (NF-L)
 - Glial fibrillary acidic protein (GFAP)

- Clinical measures – change/baseline
 - T25FW [3]
 - SSST [4]
 - 2MWT [5]
 - MSWS-12 [6]
 - 9HPT [7]
 - OSS [8]
 - STU

Statistical analysis

Descriptive statistics – baseline data

- Gaussian distribution will be inspected by normal probability plots and the Shapiro-Wilk test.
- Data will be reported as numbers (n) and percentage (%) or mean values and standard deviations (SD), and median values and interquartile range (IQR), as required, according to assumption of Gaussian distribution.

Changes between baseline and 14-days follow-up

- Gaussian distribution will be inspected by normal probability plots and the Shapiro-Wilk test.
- Change will be examined using Student's paired *t*-test (parametric) and Wilcoxon signed rank test with median values (non-parametric).

Correlations of change between baseline and 14-days follow-up

- If a change in biomarkers is demonstrated, correlations between change in biomarkers and change in clinical measures will be examined using Pearson's product-moment correlation coefficient *r* and/or Spearman's rank-order correlation coefficient ρ (rho).
- If no change in biomarkers is demonstrated, correlations between baseline data for biomarkers and baseline data for clinical measures will be examined using Pearson's product-moment correlation coefficient *r* and/or Spearman's rank-order correlation coefficient ρ (rho).

Study 4

Objective

To evaluate changes in hand and walking parameters in participants with MS following Fampridine treatment, according to the disability level.

Participants

Participants, who completed both baseline and 14-days follow-up, who followed instructions of Fampridine intake, and who did not receive Fampridine at inclusion.

Outcome measures

- Demographic measures – at baseline
 - Age
 - Gender
 - EDSS [1]
 - Disease duration
 - Sub-diagnosis (MS)
- Clinical measures – baseline and change between baseline and 14-days follow-up

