 - T25FW [3]
 - SSST [4]
 - 2MWT [5]
 - MSWS-12 [6]
 - 9HPT [7]

Statistical analysis

Descriptive statistics – baseline data

- Gaussian distribution will be inspected by normal probability plots and the Shapiro-Wilk test.
- Data will be reported as numbers (n) and percentage (%), mean values and standard deviations (SD) and median values and interquartile range (IQR), as required according to assumption of Gaussian distribution.

Definition of subgroups according to their EDSS

- Subgroup 1: Moderate walking disability (EDSS 4.5-5.5)
- Subgroup 2: Severe walking disability (EDSS 6.0-7.0)
- Comparison of subgroups at baseline will be examined using Student's unpaired *t* test (parametric) and Wilcoxon rank sum test/Mann Whitney test (non-parametric).

Changes between baseline and 14-days follow-up

- Gaussian distribution will be inspected by normal probability plots and the Shapiro-Wilk test.
- Change for all included participants, subgroup 1 and subgroup 2, respectively, will be examined using Student's paired *t*-test (parametric) and Wilcoxon rank sum test (non-parametric).
- Comparison of change scores between subgroups will be examined using Student's unpaired *t* test (parametric) and Wilcoxon rank sum test/Mann Whitney test (non-parametric).

References

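### Study 4 does not hold the parametric or non-parametric choice constant across all participants and the two EDSS subgroups, so the rows for one outcome may not be comparable

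*SAP*

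**What the plan says.** In Study 4, under the heading on changes between baseline and 14-day follow-up, the first bullet reads "Gaussian distribution will be inspected by normal probability plots and the Shapiro-Wilk test". The next bullet reads "Change for all included participants, subgroup 1 and subgroup 2, respectively, will be examined using" Student's "paired *t*-test (parametric) and Wilcoxon rank sum test (non-parametric"). A third bullet compares change scores between the subgroups with an unpaired t-test and a rank sum/Mann-Whitney test.

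The subgroups are "Subgroup 1: Moderate walking disability (EDSS 4.5-5.5") and "Subgroup 2: Severe walking disability (EDSS 6.0-7.0"). The objective is to evaluate change according to disability level.

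The section does not give:
- a significance level for Shapiro-Wilk, or a rule for when plot and test disagree;
- the set in which normality is judged (the whole group or each subgroup);
- which of the two tests is the main one;
- the summary of change to be reported. The mean or median rule, "as required according to assumption of Gaussian distribution", stands under the baseline descriptives. Studies 2 and 3 do attach a summary to the rank branch for change: "Wilcoxon signed rank test with median values (non-parametric").

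In Study 1 the SAP fixes Spearman's coefficient for its comparisons and gives the reason: "This to ensure that the parameters are the same for all comparisons".

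**The concern.** The three rows for an outcome are there to be read against each other. If the normality check is applied row by row, one subgroup can be analysed with a t-test and the other with a rank test, even when change has the same distribution in both. When change is skewed, the two tests answer different questions. If the summary follows the test, as in Studies 2 and 3, a mean change would also stand beside a median change. Part of the difference seen between disability levels would then come from the choice of statistic.

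The missing rule also lets the branch be settled after the data are seen. With plots in the check and no threshold for the test, two analysts could reasonably choose differently.

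**Working it through.** Study 4 states no sample size, alpha or power, so there is no figure of the plan's own to reproduce.

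**Inputs**
- From the SAP: cohort of 48 (administrative information); three sets and five outcomes (T25FW, SSST, 2MWT, MSWS-12, 9HPT).
- Assumed: 44 analysed, split 22/22 or 30/14; Shapiro-Wilk at 5%, applied separately in each set; both subgroups drawn from the same distribution. The distributions are Gaussian, t with 5 df (heavy-tailed, symmetric) and gamma with shape 4 (skewness 2/√4 = 1).

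**Step 1. How often the subgroups take different branches.** If Shapiro-Wilk rejects with probability p1 in subgroup 1 and p2 in subgroup 2, then

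P(split) = p1(1 − p2) + p2(1 − p1).

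- Gaussian, p1 = p2 = 0.05: 2 × 0.05 × 0.95 = 0.095.
- Skewness 1, 22/22, simulated p1 = 0.322 and p2 = 0.325: 0.322 × 0.675 + 0.325 × 0.678 = 0.217 + 0.220 = 0.44.
- Skewness 1, 30/14, simulated p1 = 0.436 and p2 = 0.198: 0.436 × 0.802 + 0.198 × 0.564 = 0.350 + 0.112 = 0.46.

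Direct counts in repeated simulations (2,500 to 6,000 runs where the number is recorded):

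| Change distribution | Subgroups differ | Three rows not all alike |
|---|---|---|
| Gaussian | 9–10% | 11–12% |
| t, 5 df | 30–34% | 35–40% |
| Skewness 1 | 42–47% | 53–60% |

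Other assumed splits (24/24, 16/32, 15/25, 12/20) give 9–10%, 26–34% and 36–48% for the subgroup column.

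**Step 2. Cause of the splits.** At skewness 1 the equal split (22/22) gives almost the same rate as the unequal one (30/14). Unequal size adds little. Most of the splitting is sampling chance in the normality test itself.

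**Step 3. Number of outcomes affected.** The expected count needs no independence assumption. It is 5 × 0.095 ≈ 0.5 outcomes if all changes are Gaussian, and 5 × 0.42 = 2.1 to 5 × 0.47 ≈ 2.4 if all have skewness 1.

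**Step 4. Whether the branch matters.** True mean change zero, n = 44, two-sided 5%, with the signed rank test as the paired rank test:
- Gaussian and t with 5 df: both tests reject in about 5%. For symmetric change the mean and median coincide, so the nulls agree.
- Skewness 1: t about 5.6%, signed rank about 9% (repeat runs 5.3–5.6% and 8.6–9.6%).

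For the summaries, a gamma variable with shape 4 has mean 4, SD 2 and median about 3.67. The mean and median of the same changes then differ by (4 − 3.67)/2 ≈ 0.16 SD. That is the gap expected between two identical subgroups if one row gave a mean and the other a median.

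**Step 5. After the fix.** With one test and one summary fixed per outcome, the chance of mixed rows is zero by construction.

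**The case against.** Four points on the other side carry weight.

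- **The selection rule is not written down.** The SAP joins the two tests with *and*. It does not say that Shapiro-Wilk decides, and *respectively* governs where change is tested, not where normality is judged. One judgement per outcome, or reporting both tests, would also fit. This stands. Still, the labels parametric and non-parametric straight after a normality check make selection the natural reading. If both tests are run, no main result is named, and the same fix applies.
- **The mean or median part is inferred.** Study 4 names only tests for change. The pairing comes from its baseline rule and from Studies 2 and 3. This stands, and it is a further reason to state the summary.
- **There is a direct comparison.** The between-subgroup bullet applies one statistic to both subgroups, whichever test is chosen. A reader might infer that the comparison by disability level is invalid. The SAP does not support that: what suffers is the side-by-side reading of the within-subgroup rows.
- **The studies are exploratory.** The SAP says so, and no confirmatory error rate is at stake. Study 1's fixed coefficient serves a formal bootstrap comparison, so it is only a loose precedent.

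Two larger readings of the size are also tempting:
- Treating the five outcomes as independent gives 1 − 0.905⁵ ≈ 39% for at least one split under Gaussian change. Four of the five measure walking, so independence is not credible.
- A strongly skewed case (log-normal, sigma 0.8) has the signed rank test rejecting in about 30% against about 8% for t. There Shapiro-Wilk rejects in over 99% of samples of 44, so the whole-group row almost always takes the rank branch, and at 22/22 the subgroups split in only about 21–22%. That figure does not describe the mixing of rows.

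**Conclusion.** The point holds as a gap in specification that is cheap to close. On its natural reading, Study 4 lets the normality check choose the test, and it does not keep the choice the same across the three rows or for the between-subgroup comparison. Under the assumed sizes and a 5% Shapiro-Wilk, two subgroups with the same distribution take different branches in about 10% of cases per outcome for Gaussian change and about 42 to 47% at skewness 1. The distortion of the null is modest (about 5.6% against about 9%) and arises only when change is skewed. The consequences are within-subgroup rows that may not be comparable and freedom for the analyst. The direct between-subgroup test is not invalidated. Subgroup sizes, distributions and threshold are all assumptions, because the SAP gives none of them.

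**What to change.** Drop the normality test as a selector; plots can stay as description. For each outcome, name one summary and one test for all participants, subgroup 1 and subgroup 2, and the matching test for the between-subgroup comparison. One example is mean change with 95% CI, paired t within groups and unpaired t between them. A rank-based choice fixed for every row would remove the mixing equally well; what matters is that it is fixed beforehand. Show the paired non-parametric result for every row as a secondary column.

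The same edit should reconcile the rank sum test, which is for independent samples but is named here for paired change, with the signed rank test named for the same purpose in Studies 2 and 3.

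The cost is a few lines of SAP wording, one extra table column, and some loss of efficiency for outcomes with heavy-tailed change. No new data are needed.
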